11.3.3 Visual Field

Visual field examinations will be assessed using automated perimetry (using either Humphrey 24-2 full threshold program or 24-2 Swedish Interactive Thresholding Algorithm [SITA] Standard, or Octopus G1 or 24-2 programs and Dynamic or Normal strategy) at screening, baseline, Week 28, Week 52, and Month 20/Exit. The same test methodology must be used throughout the entire study for a given patient. Data will be reported as normal or abnormal and the mean deviation (MD) will also be recorded in decibels (dB). Visual field MD change from baseline will be calculated for each postbaseline visit and summarized with descriptive statistics by machine type (Humphrey and Octopus respectively).

Abnormal findings may include enlargement of blind spot, superior arcuate scotoma, inferior arcuate scotoma, paracentral scotoma, nasal step, central scotoma, generalized depression, and temporal scotoma and other. A listing will be provided for patients with abnormal visual field finding(s).

The number and percent of patient eyes with a normal examination value at baseline but became abnormal at any of the follow up visit will be tabulated based on the abnormal finding category for each treatment group by cycle and across all study visits.

11.3.4 Macroscopic Conjunctival Hyperemia Assessment

Macroscopic conjunctival hyperemia assessment will be performed for each eye at all scheduled visits except on any of the 3 administration days using the following scale: 0 = none, +0.5 = trace, +1 = mild, +2 = moderate, and +3 = severe. The frequency distribution for the severity grade at each scheduled visit will be summarized by treatment group for the study eye and pooled for the fellow eye.

To summarize findings from macroscopic conjunctival hyperemia assessment, a tabulation of the number and percentage of patient eyes who had more than 1 severity grade increase (worsening, i.e., a change from 0 to 2 and above, from 0.5 to 2 and above, or from 1 to 3 and above) from the baseline at any of the follow-up visits will be summarized. Similar analyses will be performed for each treatment cycle and may be provided for findings with other severity grade increase.

11.3.5 Biomicroscopy and Ophthalmoscopy

Biomicroscopy will be performed in each eye by slit-lamp examination at each scheduled visit. Dilated ophthalmoscopy (including vitreous, optic nerve, macula, and retina periphery) and lens status assessment will be performed for each eye at Screening, Baseline, Week 12, Week 28, Week 44, Week 52, and Month 20/Exit.

All biomicroscopy and ophthalmoscopy examinations findings will be coded using MedDRA dictionary.

The number and percentage of patient eyes with biomicroscopy and ophthalmoscopy findings more than 1 severity grade increase (worsening, i.e., a change from 0 to 2 and above, or from 0.5 to 2 and above, or from 1 to 3 and above) from baseline for findings with a severity grade, or a status change from absence at baseline to presence at follow-up visit for findings under other pathology which is not associated with a severity grade, at 1 or more postbaseline visits, will be tabulated by preferred term in descending order of incidence rate. The number and percentage of eyes with any clinically significant findings will be presented (as "Overall") by treatment group for study eye and pooled for fellow eye. Similar analyses will be performed for each treatment cycle and may be provided for findings with other severity grade increase.

At follow-up visits, the lens opacity will be assessed only for eyes evaluated as phakic at baseline. The presence and severity of nuclear, cortical, and posterior subcapsular cataract lens opacities using a 3-point scale (absent, < standard photo #2, and \geq standard photo #2) will be summarized by treatment group for study eye and pooled for fellow eye by visit. The lens status will be presented as data listings and may be summarized with frequency and percent as necessary.

11.3.6 Cup/Disc Ratio

The cup/disc ratio will be evaluated using a 0.0 to 1.0 scale for each eye at visits of Screening, Baseline, Week 12, Week 28, Week 44, Week 52, and Month 20/Exit.

Change from baseline at each follow-up visit will be categorized as an improvement of 0.2 or more (≤ -0.2), no change - between 0.2 and -0.2 (> -0.2 to < 0.2), or a worsening of 0.2 or more (≥ 0.2). The number and percentage of patients in each category will be provided by treatment group for the study eye and pooled for the fellow eye.

11.3.7 Gonioscopy and Bimatoprost SR Implant Assessment

Gonioscopy will be performed to assess the iridocorneal (anterior chamber) angle for both eyes at visits as specified in the protocol. Patients presenting peripheral anterior synechiae on gonioscopy will be presented in listing.

The Bimatoprost SR implant assessment will be performed during gonioscopy examination. For patients who have implant size collected, implant size (percentage of the original material) will also be summarized based on the percentage category for each implant in the study eye by cycle and visit for bimatoprost treatment groups. The number and percentage of implants at each of 12 zones of implant location will be summarized by visit. Also, the number of patients who have implant(s) contact with corneal endothelium at any visit within a cycle will be summarized by cycle. Implant assessment will be presented as data listings for the location of implant (12 zones), status of contact with other implant(s), and status of contact with corneal endothelium.

11.3.8 Macroscopic Iris Color Assessment

Iris color will be assessed visually for each eye at Baseline, Week 12, Week 28, Week 44, Week 52, Month 16, and Month 20/Exit visits. Iris color change from baseline (No, Yes with Mild, Moderate and Severe) will be presented in listing and may be summarized as necessary.

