Adverse events will be coded using the Medical Dictionary for Regulatory Activities (MedDRA) and will be summarized for all events regardless of causality and for treatment-related adverse events. Ocular adverse events and safety variables will be tabulated by study eye and fellow eye within each treatment dose strength or group, and nonocular safety variables will be summarized by patient.

[figure not shown]
Sample Size Calculation: The sample size calculation is based on the primary efficacy analysis of the IOP for US FDA review because the sample size based on the primary efficacy analysis for other regions is expected to be smaller. Based on simulations, a sample size of 486 patients (162 per group) will provide approximately 95.1% and 83.5% power to show noninferiority (NI) of Bimatoprost SR 15 µg and Bimatoprost SR 10 µg, respectively, to timolol at all 6 scheduled timepoints based on an NI margin of 1.5 mm Hg and at 3 or more timepoints based on an NI margin of 1.0 mm Hg. Assuming a premature discontinuation rate of 5% within 12 weeks (before the primary database lock), approximately 510 patients (170 per group) are to be enrolled into this study.

Figure 1 Flowchart of Patient Participation

Approval Date: 05-Jun-2018

[figure not shown]
Table 2 Screening through Treatment Day 1

[figure not shown]
Approval Date: 05-Jun-2018

Table 3 Administration Cycle 1 Schedule of Visits and Procedures: Treatment Period Day 2 through Week 12

[figure not shown]

Approval Date: 05-Jun-2018

[figure not shown]
Table 4 Administration Cycle 2 Schedule of Visits and Procedures: Treatment Period Week 15 Through Week 28

[figure not shown]

Approval Date: 05-Jun-2018

[figure not shown]
Approval Date: 05-Jun-2018

[figure not shown]

Approval Date: 05-Jun-2018

Table 6 **Schedule of Visits and Procedures: Extended Follow Up Months 14, 16, 18, and 20**

Approval Date: 05-Jun-2018

Approval Date: 05-Jun-2018

1. Background and Clinical Rationale

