Macroscopic Iris Color Assessment: Iris color will be assessed visually at each designated visit using the appropriate assessment guide (see the Protocol Procedure Manual for further details). Macroscopic, binocular color photography will be performed at baseline to document iris color. The baseline photograph printout from each patient will be used as a comparator to assess any change in iris color at subsequent visits. A suspected change in iris color will be documented with a binocular color photograph at that visit. A binocular color photograph will also be obtained at Week 52 and a final binocular color photograph will be obtained during the Month 20/Exit visit in all patients.

Progressive changes in iris color will be photographed and compared to the last photograph taken.

Macroscopic Conjunctival Hyperemia Assessment: Macroscopic conjunctival hyperemia will be assessed using the appropriate Assessment Guide (see the Protocol Procedure Manual for further details).

Bimatoprost SR Implant Assessment: Using gonioscopy, the investigator will evaluate the Bimatoprost SR implant and the inferior iridocorneal angle.

Biomicroscopic Examination: Biomicroscopic examinations will be performed using a slit lamp. The examinations will include evaluation of the condition of the eyelids, conjunctiva, cornea, AC, iris/pupil, and lens.

Lens Assessment: Biomicroscopic findings will be evaluated for the presence and severity of nuclear, cortical, and posterior subcapsular lens opacities. See the Protocol Procedure Manual for further details.

Gonioscopy: Gonioscopic examination for eligibility at Screening (only) will be independently performed by 2 ophthalmologists as described in the Protocol Procedure Manual. The independent eligibility assessors should not share their assessments with each other until the assessment is recorded. The 2 ophthalmologists' independent eligibility assessments must confirm patient eligibility for participation in the study. Subsequent gonioscopic examinations will be performed by the study investigator.

Optic Disc Examination: The cup/disc ratio and presence of optic disc pathology will be determined using stereoscopic evaluation.

Dilated Ophthalmoscopic Examination: The stereoscopic fundus assessments should be conducted through a dilated pupil. The examinations will include evaluation of the macula, vitreous, and retina.

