7.3.3 Other Efficacy Analyses

7.3.4 Safety Analyses

The Medical Dictionary for Regulatory Activities (MedDRA) nomenclature will be used to code adverse events. Adverse events will be coded from the verbatim text into preferred term and system organ class (SOC). The number and percent of patients reporting treatment emergent adverse events will be tabulated based on the primary SOC and preferred terms. Summary tables will be generated for all adverse events regardless of causality as well as treatment-related adverse events for the entire study and by treatment cycle.

Other safety variables include vital signs (blood pressure, pulse rate, and temperature) and pregnancy test results. Ocular safety will be evaluated through assessment of visual acuity and visual field; evaluation of macroscopic bulbar conjunctival hyperemia and iris color; assessment of endothelial cell density and corneal thickness; IOP measurement, biomicroscopic and ophthalmoscopic examinations (including gonioscopy with Bimatoprost SR implant assessment, optic disc examination and dilated fundus examination); and OCT of the macula.

Ocular adverse events and safety variables will be tabulated by study eye and fellow eye within each treatment dose strength, and nonocular safety variables will be summarized by patient. A separate summary will be provided for safety events occurring after nonstudy IOP-lowering medication has been initiated.

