16.7.2 Incomplete Stop Date

The following rules will be applied to impute the missing numeric fields for an incomplete prior or concomitant medication stop date unless the stop date is marked as ongoing. If the imputed stop date is before the start date (imputed or nonimputed start date), the imputed stop date will be equal to the start date. If the stop date is marked as ongoing, the study exit date will be assigned to the missing fields. If the study exit date is not available, the last visit date will be used for imputation.

Missing Month and Day

- If the year of the incomplete stop date is the same as the year of the study exit date, the month and day of the study exit date will be assigned to the missing fields.
- If the year of the incomplete stop date is before the year of the study exit date, *December 31* will be assigned to the missing fields.
- If the year of the incomplete stop date is after the year of the study exit date, *January 1* will be assigned to the missing fields.

Missing Month Only

- If only the month is missing, the day will be treated as missing and both the month and the day will be replaced according to the above procedure.

Missing Day Only

- If the month and year of the incomplete stop date are the same as the month and year of the study exit date, the day of the study exit date will be assigned to the missing day.
- If either the year of the incomplete stop date is before the year of the study exit date or if both years are the same but the month of the incomplete stop date is before the month of the date of the study exit date, the last day of the month will be assigned to the missing day.
- If either the year of the incomplete stop date is after the year of the study exit date or if both years are the same but the month of the incomplete stop date is after the month of the study exit date, the first day of the month will be assigned to the missing day.

17.0 **CHANGES TO ANALYSES SPECIFIED IN PROTOCOL**

Two additional terms the time-matched baseline IOP (either Hour 0 or Hour 2 according to the response variable) and timepoint-by-baseline Hour 0 IOP interaction were added to the primary efficacy analysis model, but were not presented in protocol amendment 3, dated 5JUN2018.

18.0 **REFERENCES**

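### The SAP commits no by-arm count of iris color change or of gonioscopic synechiae, although the protocol says ocular safety variables will be tabulated

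*SAP*

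**What the plan says.** Protocol 7.3.4 lists the examinations by which ocular safety will be judged. Among them are "evaluation of macroscopic bulbar conjunctival hyperemia and iris color" and the examinations described as "including gonioscopy with Bimatoprost SR implant assessment, optic disc examination and dilated fundus examination". It then states: "Ocular adverse events and safety variables will be tabulated by study eye and fellow eye within each treatment dose strength". The matching sentence in the Protocol Summary reads "within each treatment dose strength or group", so Control is covered as well as the two implant doses.

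SAP 11.0 includes the iris color assessment and the gonioscopy assessment in its list of safety parameters. It sets a general rule that categorical variables are reported as counts and percentages, and that ocular assessments are analyzed by arm in study eyes, with fellow eyes pooled.

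The subsections for these two examinations say something else. On iris color, SAP 11.3.8 says: "Iris color change from baseline (No, Yes with Mild, Moderate and Severe) will be presented in listing and may be summarized as necessary". On the angle, SAP 11.3.7 says: "Patients presenting peripheral anterior synechiae on gonioscopy will be presented in listing". No summary of synechiae is mentioned, not even an optional one.

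SAP 17.0, which records departures from the protocol, names only terms added to the efficacy model: "Two additional terms the time-matched baseline IOP (either Hour 0 or Hour 2 according to the response variable") and an interaction of timepoint with baseline IOP. It says nothing about safety tabulation.

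**The concern.** Both examinations are collected to detect effects of the drug or of the implant. For iris color, Protocol 6.2 says: "The baseline photograph printout from each patient will be used as a comparator to assess any change in iris color at subsequent visits". SAP 11.3.8 schedules six post-baseline assessments (Weeks 12, 28, 44 and 52, Months 16 and 20). Gonioscopy looks at the inferior iridocorneal angle, where the implant is assessed, and SAP 11.3.7 has it done in both eyes. An acceptable safety profile after single and repeat administration is one of the two clinical hypotheses.

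A listing shows individual cases but gives no rate per arm. If the report follows the SAP subsections literally, a reader who wants the incidence of iris color change or of new synechiae in implanted eyes, set against Control study eyes, must count it from line listings. For iris color, the SAP also gives no criterion for when a summary becomes necessary, and analyses are run after each of three database locks.

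**Working it through.** The documents give no figure for this point and no arithmetic applies. The check is whether any current text commits a by-arm count, and which text governs.

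| Source | Iris color change | Synechiae on gonioscopy |
|---|---|---|
| Protocol 7.3.4 and Protocol Summary | Named; ocular safety variables to be tabulated | Gonioscopy named; same rule |
| SAP 11.0 (general rule) | Count and percentage, by arm in study eyes | Same rule |
| SAP 11.3.8 / 11.3.7 (specific rule) | Listing; summary optional | Listing; no summary mentioned |
| SAP 17.0 (declared departures) | None | None |

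1. *Do the specific subsections carry out the general rule?* No. Other subsections do. Hyperemia (11.3.4), biomicroscopy and ophthalmoscopy (11.3.5), cup/disc ratio (11.3.6) and endothelial cell density (11.3.12) each have a firm table by arm. A programmer who finds a general sentence and a specific one will normally follow the specific one, which here is the listing.

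2. *Do the other gonioscopy outputs in 11.3.7 fill the gap?* No. The committed summaries cover implant size, implant location by zone, and implant contact with the corneal endothelium. They describe the implant rather than the angle, and Control eyes have no implant, so they cannot supply a Control rate.

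3. *Does the biomicroscopy table in 11.3.5 fill it?* In part, perhaps. Protocol 6.2 includes the anterior chamber and the iris and pupil in the slit-lamp examination. The table counts ungraded findings that are newly present after baseline, and graded findings that worsen by more than one grade. An iris or angle finding recorded at the slit lamp could appear there. It is still not a table of the photograph-referenced color grade or of synechiae seen on gonioscopy.

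4. *Do the adverse event tables fill it?* Only for findings that the investigator also reports as adverse events. Those would appear among the ocular events in SAP 11.1.

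5. *Is the departure declared?* No. SAP 17.0 is limited to the efficacy model.

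The conflict therefore stands in current text, both between protocol and SAP and within the SAP. No sentence that deals specifically with either examination commits a by-arm count.

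**The case against.** The strongest reply is that SAP 11.0 already supplies the commitment. It names both examinations and requires counts and percentages by arm. On that reading the defect is an internal inconsistency and not an absence. This largely stands, and the point is put that way here, but the inconsistency still needs resolving because the subsections read as the operative instruction.

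A second reply is that SAP 4.0 places the specifications of tables and listings in a separate document, which may well contain these tables. That also stands. A reader might infer that no table of either finding will ever be produced. The documents do not support this: the specifications are unseen, an iris color summary is expressly permitted, and the adverse event and biomicroscopy tables may pick up some cases. The adverse event definition in Protocol 9.1.1 is broad, covering any unfavorable and unintended sign, and SAP 11.1 also allows an optional grouping of events associated with prostaglandin analogs.

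A reader might also infer that the synechiae listing mixes pre-existing with new cases. SAP 11.3.7 does not describe the columns, visits or baseline flags of that listing, so this cannot be shown. The abbreviation for peripheral anterior synechiae is in the protocol glossary, and parts of the entry criteria are blacked out, so whether eyes with baseline synechiae could enter cannot be judged.

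Finally, Protocol 7 leaves the details of all analyses to the analysis plan, and by-arm counts could be worked out from listings and arm sizes. Both are true and both lower the severity. Delegating detail does not, however, explain an optional summary or a listing where the protocol says variables will be tabulated.

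**Conclusion.** The concern holds in limited form. The SAP subsections for iris color and gonioscopic synechiae commit listings where the protocol and the SAP's own general rule call for tabulation, and the difference is not declared in SAP 17.0. As written, no by-arm count from either examination is firmly committed.

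Severity is low. Two descriptive safety summaries are affected. No hypothesis test, error rate or efficacy result depends on them, and the data are already being collected. This is a reporting matter and involves no clinical management rule.

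The conclusion assumes that the specific subsections override the general rule in SAP 11.0, and that the unseen table specifications do not already settle the matter. If those specifications contain both tables, only the SAP wording needs to be brought into line. Nothing here indicates how often either finding will occur.

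**What to change.** In SAP 11.3.8, replace the optional summary with a firm one, for example: *Eyes with any change in iris color from baseline will be tabulated as number and percentage, classified by worst severity, by treatment arm in study eyes and with fellow eyes pooled.*

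In SAP 11.3.7, add: *Among eyes with no peripheral anterior synechiae at baseline, the number and percentage with synechiae at any post-baseline visit will be tabulated in the same layout.*

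Keep both listings. The layout follows the fellow-eye pooling in SAP 11.0. If the sponsor prefers listings only, SAP 17.0 should say so as a departure from Protocol 7.3.4. Macular OCT in SAP 11.3.9 has the same optional wording and could be reviewed in the same amendment.

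The cost is two SAP sentences and two more descriptive safety tables from data already collected, with no new assessments.

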11.3.9 Optical Coherence Tomography of the Macula

Optical coherence tomography (OCT) of the macula will be performed to assess macular edema in each eye at Screening, Week 52, and Month 20/Exit visits. Foveal central subfield (μm) from OCT data and change from baseline will be presented in listing and may be summarized as necessary.

11.3.10 Anterior Segment Optical Coherence Tomography (AS-OCT)

Anterior segment optical coherence tomography (AS-OCT) will be performed for both eyes at Screening for patients' iridocorneal angle eligibility before protocol amendment 2. The OCT images will be sent to a reading center to perform quantitative measurements of the patient inferior iridocorneal angle. If in the investigator's opinion the patient's angle size may have changed, an unscheduled AS-OCT may be performed prior to retreatment. Inferior angle measurements will be presented by data listing.

11.3.11 Pachymetry

Corneal thickness using ultrasound (contact) pachymetry will be performed on the central cornea for each eye at Screening, Week 12, Week 28, Week 44, Week 52, and Month 20/Exit. At each examination, 3 measurements of central corneal thickness (CCT) and associated standard deviation will be reported, and the average of the 3 measurements will be calculated and used for analysis. CCT baseline and changes from baseline will be summarized descriptively by treatment group for study eye and pooled for the fellow eye. In addition, CCT raw values will be summarized descriptively for each visit.

